## II. Objectives and Endpoints

- a. The primary endpoint will be assessed comparing GRA responses between sham and PTNS groups at one week ( $\pm$  3 days) post induction. This comparison will also be made for all other visits using t-tests or chi-square tests, as appropriate.
- b. Secondary endpoints will include comparisons between sham and PTNS groups looking at variables in the 3-day voiding diary and OABq-SF at one week ( $\pm$  3 days) post-induction. Voiding diary variables include frequency, nocturia, degree of urgency, and urge incontinent episodes. Changes from baseline will also be analyzed.

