Consented patients will complete the Overactive Bladder Questionnaire Short Form (OAB-q SF), 3-day voiding diary and enrollment questionnaire (demographics, medical history, concomitant medications, etc.) prior to study enrollment. A urinalysis via urine dipstick and pregnancy test (for women of child bearing potential) will be performed at screening. If the urinalysis is positive for leukocytes a urine culture will be sent. Patients with a positive urine culture may be treated per standard of care by the study physician. After treatment is completed, a repeat urine will be checked. If repeat urinalysis is negative, the subject will be allowed to complete the voiding diary and continue with study activities. The diary will be collected and reviewed at the first scheduled treatment visit (within 21 days from screening visit). If the patient meets the eligibility criteria, they will be randomized (1:1) into the sham or accelerated PTNS group.

Our goal is to have patients complete all three treatments within one week (7 days) but as there are always impedances (scheduling conflicts, illness, etc.) we will allow patients to complete all treatments within 2 weeks (14 days) if necessary. Patients will be allowed back-to-back treatments (i.e. two days in a row) if they should elect to do so. Adverse events and concomitant medications will be assessed at each treatment whether sham or active PTNS. GRA will be gathered at each visit beginning with the second induction treatment.

After completing the one-week induction consisting of three active or sham treatments, patients will receive a phone call three days ( $\pm$  1 day) after the last treatment to assess for any adverse events as well as remind them to start filling out their 3 day diary if they have not already begun to do so. This will also serve as a reminder phone call for their upcoming appointment.

One week post-induction ( $\pm$ 3 days), patients will return for an office visit. OAB-q SF, GRA and 3-day voiding diary will be collected. We will also assess for adverse events and concomitant medications at this visit. A blinding assessment questionnaire will be administered as well. A urinalysis will be completed.

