At 4, 8, and 12 weeks post-induction ( $\pm$  7 days), patients will return for follow-up appointments. Non-modified OAB-q SF, GRA and 3-day voiding diary will be collected and a urinalysis completed. Maintenance treatments (sham or active PTNS depending on treatment arm) will be given. Maintenance treatment will consist of a 30 minute treatment per standard of care. We will also assess for adverse events and concomitant medications at each of these visits.

After all study activities are complete, patients will be un-blinded at week 12 marking the end of the study. Those who were in the sham arm will be offered the opportunity to continue on to the open label phase of the study. Subjects in the open label phase will be offered the same accelerated treatments as those in the initial active PTNS treatment group. They will have up to 12 weeks to decide if they would like to continue on to the open label phase. This option will also be offered to those who had been previously randomized to the Sham group prior to the protocol amendment, even if they have completed their visit schedule. The follow up schedule will also be conducted in the same manner. Either of the groups can be offered re-induction per insurance requirements if they elect to do so with their

physician or can seek alternative treatments (BTX, sacral neuromodulation, etc.) per standard of care.

Our goal is to have patients complete all three open label treatments within one week (7 days) again, as there are always impedances (scheduling conflicts, illness, etc.) we will allow patients to complete all treatments within 2 weeks (14 days) if necessary. Patients will be allowed back-to-back treatments (i.e. two days in a row) if they should elect to do so. Adverse events and concomitant medications will be assessed at each treatment whether sham or active PTNS. GRA will be gathered at each visit beginning with the second induction treatment.

After completing the one-week open label induction consisting of three active treatments, patients will receive a phone call three days ( $\pm$  1 day) after the last treatment to assess for any adverse events as well as remind them to start filling out their 3 day diary if they have not already begun to do so. This will also serve as a reminder phone call for their upcoming appointment.

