## V. Eligibility Criteria

### Inclusion criteria:

- Women and men  $\geq$  18 years of age
- Self-reported failed conservative care of behavioral modifications and / or oral medications
- A score of  $\geq$  4 on question 1 of the OAB-q symptom bother short form completed by the patient at screening
- Average urinary frequency of  $\geq$  8 voids per day as recorded on initial 3-day voiding diary
- Self-reported bladder symptoms  $\geq$  3 months
- On a stable dose of antimuscarinics/beta-3 agonists for  $\geq$  4 weeks, and willing to remain on the medication for the duration of the study OR discontinued antimuscarinics/beta-3 agonists for  $\geq$  2 weeks
- Capable of giving informed consent
- Ambulatory and able to use toilet independently without difficulty
- Capable and willing to follow all study-related procedures

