## VI. Data Analysis

A biostatistician will perform all statistical analyses using SAS or similar statistical software. Descriptive statistics will be calculated. A completer analysis will be conducted for those who finish the study per protocol. The primary endpoint will be assessed comparing GRA responses between sham and PTNS groups at one week ( $\pm$  3 days) post induction. This comparison will also be made for all other visits using t-tests or chi-square tests, as appropriate.

Secondary endpoints will include comparisons between sham and PTNS groups looking at variables in the 3-day voiding diary and OABq-SF at one week ( $\pm$  3 days) post-induction.

Changes from baseline will also be analyzed. This comparison will also be made for all other visits using appropriate statistical tests.

Other statistical analyses will be completed as appropriate.

An intent to treat analysis which will identify any subject not assessed at 12 weeks post-induction as a failure will be conducted; a minimum of 1 induction treatment will be required to be included in the analysis.

Calculating Sample Size:

A sample size estimate of approximately 64 patients, 32 per study arm, was calculated using the Z test with pooled variance using a 58.3% responder rate in the PTNS group and a 21.9% responder rate in the sham group with a 5% significance level and 80% power; this also accounts for a 10% drop out rate. (Peters et al reported 58.3% and 21.9% responder rates for PTNS and sham groups respectively for an as-followed completer analysis and 54.5% and 20.9% responder rates for PTNS and sham groups respectively with an intent to treat analysis. We used the as-followed responder rates in calculating our sample size.)

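### The secondary diary and OABq-SF endpoints have no stated lead analysis and no baseline adjustment, although the baseline values are already to be collected; a modest gain at almost no cost

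*Combined protocol and SAP*

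**What the plan says.** VI. Data Analysis of the combined protocol and SAP sets out the secondary comparison: "Secondary endpoints will include comparisons between sham and PTNS groups looking at variables in the 3-day voiding diary and OABq-SF at one week". It continues: "Changes from baseline will also be analyzed. This comparison will also be made for all other visits using appropriate statistical tests". II. Objectives and Endpoints lists the variables and adds the change analysis in the same item: "Voiding diary variables include frequency, nocturia, degree of urgency, and urge incontinent episodes. Changes from baseline will also be analyzed".

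Neither section names a baseline covariate or a regression model. The only tests named are in the GRA sentence: "This comparison will also be made for all other visits using t-tests or chi-square tests, as appropriate".

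Baseline collection is planned in III. Methodology: "Consented patients will complete the Overactive Bladder Questionnaire Short Form (OAB-q SF), 3-day voiding diary and enrollment questionnaire" before enrollment. Two entry criteria in V. Eligibility Criteria are read from these instruments: a score "on question 1 of the OAB-q symptom bother short form completed by the patient at screening", and at least 8 "voids per day as recorded on initial 3-day voiding diary". The same instruments return at weeks 4, 8 and 12: "Non-modified OAB-q SF, GRA and 3-day voiding diary will be collected and a urinalysis completed".

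**The concern.** The plan gives two ways to analyse each secondary variable and does not say which is the main result. In VI. Data Analysis the natural reading is that both are compared between arms, because the sentence on changes is followed by one that carries the comparison to the other visits. II. Objectives and Endpoints leaves that open.

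Two things are at stake.

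- **Precision.** A one-week comparison run without the baseline value ignores information that is to be collected anyway. A simple change score uses the baseline with a fixed weight of 1, which can be better or worse than not using it at all.
- **Interpretation.** If both tests are run, one may fall below 0.05 and the other not, with no stated rule for which result to read.

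The trial is sized on GRA responders, so precision on these endpoints was not planned for.

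**Working it through.** **1. The plan's own figure.** The only sample-size figure is for GRA. With responder rates of 0.583 and 0.219 (mean 0.401), two-sided 5%, 80% power and pooled variance:

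n = [1.96·√(2·0.401·0.599) + 0.842·√(0.583·0.417 + 0.219·0.781)]² / 0.364² ≈ 27.2, so 28 per arm.

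28 / 0.9 = 31.1, so 32 per arm and 64 in total. The stated N reproduces and does not depend on this point.

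**2. Inputs for the secondary endpoints.** From the documents: 32 per arm less 10% drop out, 32 × 0.9 = 28.8, taken as n = 29. Assumed, because the documents give none of them: roughly normal variables; true difference d, in SDs of the one-week value; baseline to one-week correlation r = 0.3, 0.5, 0.7; ratio of baseline SD to one-week SD k = 0.7 or 1.

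**3. Variance of the between-arm difference, relative to the one-week value.**

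- One-week value: 1 (56 df)
- Change from baseline: 1 + k² − 2rk (56 df)
- ANCOVA: (1 − r²)(1 + 1/(2n − 4)) (55 df)

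Example with r = 0.5: change is 1.00 at k = 1 and 0.79 at k = 0.7; ANCOVA is 0.75 × (1 + 1/54) = 0.764. At r = 0.3 and k = 1 the change score has variance 1.40, worse than ignoring baseline.

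**4. Power, two-sided 5%.** Noncentral t with noncentrality d / √(2V/29), where V is the relative variance above. Power in %, gains in percentage points from unrounded values; *better* means the better of the two unadjusted analyses.

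| d | r | One-week | Change, k=1 | Change, k=0.7 | ANCOVA | Gain over one-week | Gain over better, k=1 | Gain over better, k=0.7 |
|---|---|---|---|---|---|---|---|---|
| 0.5 | 0.3 | 46.5 | 35.3 | 44.0 | 49.3 | 2.9 | 2.9 | 2.9 |
| 0.5 | 0.5 | 46.5 | 46.5 | 55.8 | 57.2 | 10.7 | 10.7 | 1.4 |
| 0.5 | 0.7 | 46.5 | 67.6 | 74.5 | 73.7 | 27.3 | 6.2 | −0.8 |
| 0.65 | 0.3 | 68.2 | 53.8 | 65.2 | 71.4 | 3.3 | 3.3 | 3.3 |
| 0.65 | 0.5 | 68.2 | 68.2 | 78.1 | 79.5 | 11.3 | 11.3 | 1.3 |
| 0.65 | 0.7 | 68.2 | 88.1 | 92.6 | 92.1 | 24.0 | 4.0 | −0.5 |

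The gain over the better unadjusted analysis is −0.5 to +4.8 points at d = 0.3 and 0 to +2.7 at d = 1.0. The small losses occur at r = k = 0.7, where the change score happens to use the ideal weight and ANCOVA pays only for estimating it.

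**5. Effect of the entry criterion on frequency.** Requiring at least 8 voids per day narrows baseline frequency. Assume that untruncated baseline frequency is normal with mean 10 to 12 and SD 3. With a = (8 − mean)/3 and λ = φ(a)/(1 − Φ(a)), the share of baseline variance kept is v = 1 + aλ − λ², which is 0.53 at mean 10 and 0.73 at mean 12. The correlation becomes r√v / √(r²v + 1 − r²): 0.5 falls to 0.39–0.44, and 0.7 to 0.58–0.64.

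**6. Two tests on one variable.** Simulation under the same assumptions, 40,000 trials per cell. With no true effect, at least one of the two unadjusted tests is significant in 8 to 9% of trials. At d = 0.5, one is significant and the other not in 23 to 40% of trials; part of that is simply their different power. With a true effect, no simulated trial was significant in opposite directions.

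**The case against.** The strongest reply is that the plan does use baseline. Changes from baseline are in both sections, and the open wording on tests could cover ANCOVA. The ordinary reading of *also* is that the one-week comparison leads and change supplements it.

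Much of this stands. A reader might infer from the 27-point gain that the plan gives up that much power. It does not: that figure sets ANCOVA against a one-week comparison alone, and at the same correlation the planned change score recovers most of the difference. The fair comparator is the better of the two unadjusted analyses. What remains is that nobody knows beforehand which of the two will be better, and ANCOVA is never materially worse than either on this grid. The lead can be inferred, but it is not stated.

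A reader might also infer a false-positive rate of 8 to 9%. That would require reporting only the more favourable test, which the plan does not propose.

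The reply is also right that the calculation covers only frequency and OABq-SF. It does not support prescribing negative binomial or proportional-odds models for the other three diary variables. In a small simulation of a negative binomial model with a Wald test at 29 per arm (assumed means of 3 to 6 per diary and dispersion 0.8 to 2, 800 runs per cell), false positives were 6 to 8%, and with near-Poisson counts 12% of fits did not converge.

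Finally, the entry criteria secure only average frequency and OAB-q SF question 1. Collection of the other baseline items is planned, but their completeness is not guaranteed.

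**Conclusion.** The point holds as a modest gap in precision and pre-specification. The lead secondary analysis is not stated, and baseline adjustment is not specified although the baseline data are planned.

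For roughly normal variables at 29 per arm, with r from 0.3 to 0.7 and k from 0.7 to 1, ANCOVA is worth about −1 to +11 percentage points of power against the better unadjusted analysis at d = 0.5 to 0.65. Against a one-week comparison that ignores baseline it is worth about 3 to 27 points at d = 0.5. For frequency the gain is probably in the lower part of the range, because the entry criterion narrows baseline. No size is claimed for nocturia, degree of urgency or urge-incontinent episodes.

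A reader might go further and conclude that the unadjusted comparisons are biased, or that the trial's main result is weakened. The documents support neither. Allocation is randomised 1:1, so both unadjusted contrasts are unbiased, and the primary endpoint and N=64 rest on GRA responses.

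**What to change.** In VI. Data Analysis, with II. Objectives and Endpoints to match, state that:

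- for frequency and OABq-SF, the lead between-arm analysis is the one-week value by ANCOVA, with the baseline value of the same variable as covariate, and the same model is used at weeks 4, 8 and 12;
- for nocturia, degree of urgency and urge-incontinent episodes, the lead one-week comparison also adjusts for baseline, by a method that the trial's biostatistician fixes before unblinding (for example rank-based ANCOVA, or a count model with small-sample inference);
- unadjusted values and changes from baseline are supportive.

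The cost is a few sentences, a few lines of programming and, for ANCOVA, one degree of freedom (about 1 power point or less). No new data or patients are needed. The change does not settle multiplicity across variables and visits, or the choice between the completer and intent-to-treat sets.

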## III. Methodology

The aim of this study is to determine the efficacy of an accelerated course for percutaneous tibial nerve stimulation (PTNS) induction. The standard 12 weekly induction treatments may be a patient burden and a more rapid induction may speed up symptomatic improvement.

We anticipate enrolling 64 patients, in this randomized trial, 32 in each study arm. Patients will be recruited from Beaumont's Women's Urology Center, as well as private Urology offices. Eligible patients will be consented and randomized into 1 of 2 groups. Patients will be enrolled in the study and randomized:

- After all screening activities have occurred and it has been determined that the patient meets all inclusion criteria without the presence of exclusionary criteria.
- After the patient agrees to enroll and comply with the study protocol, regardless of study group assignment.

Patients will be randomized 1:1 to active PTNS treatment or Sham treatment

The process of randomization will be as follows:

- Randomization will be performed using a table of random numbers. Randomization envelopes will be provided by the study's biostatistician. Randomization assignment will be to either active PTNS treatment or Sham treatment. The randomization envelopes will be securely stored in a locked cabinet. The Research Coordinator(s) will ultimately be responsible for maintaining the confidentiality and security of the randomization envelopes.
- The biostatistician will prepare more envelopes, if necessary.
- After the participant is randomized, staff will complete the ***Subject Enrollment and Randomization Log***. The log may be stored in the locked cabinet with the envelopes. Ultimately the log will be stored in the regulatory binder.

All patients who enroll will be seen and treated at the Beaumont Urology clinical research suite.

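### The missing-data rule cannot be applied to the diary and OABq-SF endpoints, no analysis set is assigned to them, and the completer analysis would leave out week-1 values already collected

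*Combined protocol and SAP*

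**What the plan says.** Section VI (Data Analysis) names two analyses. One covers completers, meaning patients who finish the study per protocol. The other is described as follows: "An intent to treat analysis which will identify any subject not assessed at 12 weeks post-induction as a failure will be conducted". Membership of the intent-to-treat set requires at least one induction treatment.

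The secondary endpoints are diary variables and OABq-SF, compared between arms one week after induction. Section II lists the diary items: "Voiding diary variables include frequency, nocturia, degree of urgency, and urge incontinent episodes". Changes from baseline are also planned. For the later visits Section VI adds: "This comparison will also be made for all other visits using appropriate statistical tests".

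Section III (Methodology) has the diary and OAB-q SF collected at the one-week visit and again at weeks 4, 8 and 12. It places the end of the blinded study at week 12.

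**The concern.** *Failure* is a code for a yes/no outcome. It fits a GRA responder analysis. It gives no number to enter for voids per day, nocturia, leakage episodes or a questionnaire score. Section I quotes a success definition based on percentage reductions, but it describes published studies and is not adopted as an endpoint here. So the one missing-data rule in the plan cannot be carried out for the secondary endpoints.

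The other stated analysis is the completer analysis. Completion is settled at week 12, while the secondary endpoint is measured at week 1. A patient who gives a diary and an OABq-SF score at week 1 and leaves at week 6 is outside that set. A collected endpoint value is then lost because of a later event. If each visit is also tested on its own, that patient's week-1 and week-4 values contribute nothing to the week-8 and week-12 comparisons.

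At stake are some precision at week 1 and, if patients doing poorly leave one arm more often than the other, a biased treatment difference. Because set, test and missing-data handling are all open, they could also be settled after the data have been seen.

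**Working it through.** **1. The plan's sample size.** Inputs from Section VI: planning responder rates of 58.3% (PTNS) and 21.9% (sham), power of 80% at the 5% level, and a size that "was calculated using the Z test with pooled variance". Allocation is 1:1 (Section III). Sidedness is not stated; two-sided is assumed. With mean rate (0.583 + 0.219)/2 = 0.401:

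n = [1.960 × √(2 × 0.401 × 0.599) + 0.842 × √(0.583 × 0.417 + 0.219 × 0.781)]² / (0.583 − 0.219)² = 27.2, so 28 per arm.

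Dividing by 1 − 0.10 gives 31.1, so 32 per arm and 64 in total. This matches the plan and is not disputed. It concerns GRA only; the documents give no SD or effect size for the secondary endpoints, so what follows is in SD units.

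**2. Precision at week 1.** The plan says of its size that "this also accounts for a 10% drop out rate". Completers per arm: 32 × 0.90 = 28.8.

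- If every dropout leaves after the week-1 visit, the standard error ratio is √(32/28.8) = 1.054, about 5% wider. The detectable difference at 80% power moves from 2.80 × √(2/32) = 0.70 SD to 2.80 × √(2/28.8) = 0.74 SD.
- If half leave before week 1 (an assumption), 32 − 1.6 = 30.4 week-1 values exist per arm and the ratio is √(30.4/28.8) = 1.027.
- The plan does not time the dropout, so 5% is an upper bound.

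**3. Bias at week 1, by simulation.** Assumptions, none of them in the documents: 32 per arm, normal scores with SD 1, and a true difference of 0.50 SD. In an arm with selective loss, dropout after week 1 depends on the week-1 score (odds ratio 2.7 per SD worse, about 13% dropout). An arm without it loses 10% at random.

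| Dropout related to outcome | Completers show | All observed week-1 values show |
|---|---|---|
| Sham arm only | 0.38 to 0.39 SD | 0.50 SD |
| Active arm only | 0.61 to 0.62 SD | 0.50 SD |
| Both arms, relative to own arm's mean | 0.49 SD | 0.50 SD |
| Both arms, on a common scale | 0.47 SD | 0.50 SD |

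These results vary by about 0.01 between runs. In the one-arm cases the error is about 0.12 SD, or 0.12/0.50 = 24%. The estimate's standard error is √(2/28.8) = 0.26 SD, so the bias is less than half of it. With no true difference, the completer t-test rejects about 7% of the time instead of 5%.

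**4. Equal and unequal losses.** In a separate simulation with outcome-related loss of 3 patients per arm, completers show no bias (0.00 SD) and a type I error of about 5 to 6%. With 6 lost from one arm and none from the other (6/32 = 19% in that arm), bias is about 0.18 SD and type I error about 11%. All observed week-1 values give no bias and about 5% in both cases.

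**5. Later visits.** No bias was computed for weeks 4 to 12. The point there is structural: a test confined to one visit cannot use what a dropout recorded before leaving.

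**The case against.** A reader might infer that the plan sends the secondary endpoints to completers, that early data are to be discarded, and that every secondary result rests on a subset formed after randomization. The documents do not say so. No sentence assigns these endpoints a set. The intent-to-treat description has two separable parts, a coding rule and a membership rule. Only the coding rule breaks down for scores; the requirement of at least one induction treatment could hold every observed week-1 value. Testing all available values at each visit is an ordinary reading of the sentence on other visits, and the plan leaves room for further analyses as appropriate. This part of the objection stands, so the exclusion is a consequence of the completer analysis and not an instruction.

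A reader might also take an error of about a quarter as the expected bias. That does not hold either. It needs outcome-related loss in one arm only, with dropout there above the planned 10%.

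It can further be said that one sentence admitting all observed values would remove the simulated week-1 bias without a mixed model. That is correct for week 1. The case for the model rests on weeks 4, 8 and 12, where it uses dropouts' earlier values and separate tests do not. The objection that a model without the baseline value, or one continuous model for every diary item, would be incomplete also stands; the fix allows for both.

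**Conclusion.** The concern holds in limited form. The only missing-data rule cannot be applied to diary variables or OABq-SF scores, and no analysis set is assigned to them. The completer analysis would exclude week-1 values already in hand, and separate tests by visit leave dropouts' earlier values unused.

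The size is modest: at most about 5% wider standard errors at week 1 under the planned 10% dropout. Bias is about 0.12 SD against a true 0.50 SD if outcome-related dropout is confined to one arm, in a direction that depends on the arm, and near zero if dropout is similar in both. The effect size, odds ratio and dropout pattern are assumptions. Only secondary endpoints are affected. The change is worth making because it is cheap and settles the method before the data are seen.

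**What to change.** In Section VI:

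- State that the failure rule applies to GRA only.
- Analyse each continuous secondary endpoint in all randomized patients with at least one post-baseline value, in one repeated-measures mixed model over weeks 1, 4, 8 and 12. Include baseline value, arm, visit and arm-by-visit, with unstructured covariance.
- Take the week-1 contrast as the secondary endpoint and read the later visits from the same model.
- Use a count or ordinal version for urge incontinence episodes and degree of urgency if these are skewed or ordinal.
- Keep the completer analysis as a sensitivity analysis.

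The cost is one paragraph and standard SAS code, with no new data, visits or patients. The small downside is that the model relies on a missing-at-random assumption, which should be stated.
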